6.5 Ancillary Study Visits

6.5.1 Weekly Ancillary Study Visits

Subjects who agree to participate in the ancillary study will be randomized to standard care or behavioral/motivation intervention (once weekly visits with investigator +2 phone calls per week) to evaluate durability of ET effects.

6.5.2 Final Ancillary Study Visit

The final ancillary study visit will occur 8-10 weeks after ET Visit 36. This visit will include a safety assessment, DEXA, cardiopulmonary exercise test, AXM return and final data download, repeat QOL assessment, Borg symptom severity (effort and dyspnea scores) will be recorded during standardized exercise training at a common objective workload, 2 mph on treadmill at 2° grade for 5 minutes.

6.5.3 Optional MRI and Muscle biopsy Study

Subjects who agree to participate in the MRI ancillary study will undergo contrast MRI at the beginning of the trial (after consent but prior or as close to the start of exercise training) and again

at the conclusion of the drug intervention portion of the trial (within 2 weeks). Subjects who agree to participate in the optional muscle biopsy study will undergo a muscle biopsy at the beginning of the trial (after consent but prior or as close to the start of exercise training) and again as close to the end of ET as possible.

Study Assessments:

Accelerometry (AXM): daily activity will be assessed using externally-worn hip accelerometers (GT3XP-BTLE, Actigraph; Pensacola, FL), which participants will receive along with a belt at Visit 1. The belt will be tailored by the site study coordinators to provide a comfortable fit over or under clothing. Participants will wear the belt continuously throughout the study, including while sleeping. The device will be removed only for bathing or swimming.

Baseline (pre-intervention) daily activity will be assessed from AXM data obtained following Visit 1 but prior to ET1 (1-2 weeks). AXM data will be downloaded from the devices and units exchanged (to ensure adequately charged batteries) at least every 4 weeks. Mayo health system participants will be sent home with an accelerometer charger and instructed to charge the device daily while it is off for showering or bathing. At the final visit on-trial accelerometer data will be downloaded.

Subjects will be encouraged to walk for at least 30-60 minutes on non ET-days and will record outpatient activity levels in a log book to compare with accelerometer recorded activity levels. Subjects with low reported activity in log books will be encouraged to increase activity levels.

Assessment of Exercise tolerance will be performed by measuring Borg perceived effort (6-20 scale) and dyspnea (0-10 scale) scores during matched, low-level submaximal effort (2 mph on treadmill at 2° grade for 5 minutes). This assessment will be performed at Visit 1, on the third ET visit of each week (i.e. ET3, ET6, ET9...up to ET36), and at Visit 2. Submaximal exercise assessment of symptom severity at Visits 1 and 2 will occur *after* the primary endpoint assessment of peak exercise capacity. Patient-reported activity levels will be assessed by the IPAQ questionnaire, which will be completed at the screening visit and final endpoint visit (week 12).

Measurement of QOL will be performed every other week at ET sessions using the Kansas City Cardiomyopathy Questionnaire (KCCQ).^{56, 57} The KCCQ score reflects clinical status in HF with high fidelity;^{56, 57} the score changes rapidly with clinical improvement or deterioration,^{58, 59} is strongly associated with outcome,⁶⁰ and performs equally well in HFpEF and HFrEF.⁶¹ The SF36 will be completed at the screening visit and final endpoint visit (week 12).

Endothelial function will be assessed at Visit 1 and Visit 2 using digital arterial tonometry (reactive hyperemia peripheral arterial tonometry, RH-PAT, EndoPAT, Itamar Medical).⁹ These noninvasive assessments are routinely performed for both research and clinical care purposes. Changes in activity level, QOL and symptoms will then be correlated with changes in microvascular endothelial function (RH-PAT).

Assessment of Exercise capacity will be performed at Visit 1 (pre drug) and Visit 2 (week 10 for Stage II of study) using expired gas analysis in the laboratory of [name] (Joseph 4).

Subjects participating in the additional ancillary study will also undergo an additional cardiopulmonary exercise test at the final ancillary study visit. Participants will undergo standard, maximal effort cardiopulmonary testing on a semi-recumbent cycle ergometer to maximal subjective effort level with assessments of gas exchange as described below:

- Measurement of Gas Exchange and Ventilation will be performed during exercise testing to measure the volumes of VO₂, carbon dioxide produced (VCO₂), breathing frequency (fb), tidal volume (VT), minute ventilation (VE), partial pressure of end-tidal oxygen and carbon dioxide (PETO₂ and PETCO₂), and derived variables (e.g., respiratory exchange ratio, VE/VCO₂, etc.) using a low resistance, open circuit, automated metabolic system (Medical Graphics Co., St. Paul, MN) integrated to a mass spectrometer (Perkin Elmer, model 1100) as we have previously described.^{4,9,13,35,36}
- Cardiac Output (CO) will be measured at rest and during exercise by the acetylene (C₂H₂) wash-in technique first described by Stout et al., refined by Gan et al. and Nielson et al. and validated against direct Fick in our laboratory.⁴⁵⁻⁴⁸

Echocardiography will be performed at rest and during exercise at Visit 1 and Final Visit to estimate central cardiac hemodynamics and ventricular function, including EF, Doppler-estimated pulmonary artery systolic pressure, and LV filling pressures (E/e' ratio).

Dual Energy X-ray Absorptiometry (DEXA) will be performed at the first and final visit in the primary study, and for subjects participating in the ancillary trial, at the final visit of that component, to measure changes in body composition during the trial.

Magnetic Resonance Imaging (MRI) will be performed in subjects participating in the optional MRI substudy to measure cardiac structure and function as well as stiffness along with quantification of central and peripheral adipose tissue. As part of the MRI examination we will measure intramyocardial fat content using multiecho Dixon water and fat separated imaging with variable projection (VARPRO). We will also measure interstitial myocardial fibrosis by extracellular volume (ECV) using the MOLLI TI mapping sequence. These additional cardiac MRI measurements will be analyzed offline by our external collaborators, from completely de-identified MRI scan data. No personal health information will be included in the scans that are transmitted for external analysis.

Muscle Biopsy

Will be performed in subjects participating in the optional muscle biopsy substudy to tell us about what improvements we see in the leg muscles, and specifically in the mitochondria of leg muscles

Biological Samples

Venous blood samples will be collected at baseline, week 4, 8, and 12 to assess clinical stability (NT-proBNP) and safety (blood methemoglobin levels). Methemoglobin levels will be used as safety markers during the study and will be shared with the DSMB. All female subjects of childbearing potential will undergo a urine pregnancy test at study enrollment and end of study.

7 Statistical Plan

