We have shown that patients with HFpEF develop marked increases in cardiac filling pressures, PA pressures, and inadequate CO reserve during exercise, and that each of these abnormalities can be improved during submaximal exercise by acute infusion of NO₂. (please refer to preliminary studies related to Aim 1, above). In addition, our group has shown that in subjects with HFpEF, the degree of NO-cGMP impairment, assessed by the reactive hyperemic index response to upper stage cuff occlusion is directly related to more severe symptoms of dyspnea and fatigue during matched submaximal exercise (Figure 9, n=31).⁹ Thus, enhancing NO-cGMP signaling with NO₂ may improve symptoms of exercise intolerance both by improving central pressures and cardiac output as well as by improving microvascular endothelial function, and in so doing, improve daily activity levels.

[figure not shown]

Figure 9: [A] Compared to controls (gray), subjects with HFpEF (black) display less flow mediated dilation (FMD) after upper arm cuff occlusion release. Worsening FMD (lower reactive hyperemia index) is associated with lower peak VO₂ [B] and more severe symptoms of fatigue [C] and dyspnea [D] during low-level exercise (20W).

[figure not shown]

Figure 10: Example data from a HFpEF subject showing averaged arbitrary accelerometry units (Y axis) vs time (X axis) over a duration of 42 days.

Accelerometry is the primary endpoint for a recently-completed NHLBI-sponsored trial in which Mayo was the lead center, testing whether isosorbide mononitrate improves daily activity tolerance in people with HFpEF in a double-blind crossover trial. Our coordinating center has been the leading enroller in this trial, and we have acquired high quality accelerometer data from all participants enrolled (Figure 10). Subjects have reported no difficulties maintaining the devices on throughout the course of the day and initial analysis of data quality reveals very little missing data.

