- Our **primary hypothesis** is that combination of NO₂⁻ and ET will be associated with greater improvement in daily activity levels compared to ET with placebo. Our **secondary hypotheses** are that combination of NO₂⁻ and ET will be associated with improvement in symptoms of dyspnea and fatigue, improved tolerability to ET, enhanced endothelial function and better QOL compared to ET with placebo.

3 Study Design

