3.3 Secondary Study Endpoints

Cardiac output reserve, peak exercise workload, rest and exercise hemodynamics assessed by echocardiography, Borg dyspnea and fatigue scores recorded during ET, endothelial function assessed by tonometry, QOL assessed by the Kansas City Cardiomyopathy Questionnaire and body composition assessed by dual energy X-ray absorptiometry (DEXA). Cardiac structure and function will be assessed by cardiac MRI and adipose content will be assessed by MRI in subjects participating in the optional MRI substudy. The muscle biopsy will tell us about what improvements we see in the leg muscles, and specifically in the mitochondria of leg muscles.

There will be ancillary trial endpoints to assess QOL, Borg symptom scores, DEXA, AXM data, and exercise capacity following completion of the main trial, comparing subjects randomized to usual care or behavioral/motivation intervention.

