7.1 Statistical Overview

7.2 The full statistical details for this protocol are documented in the supplementary Statistical Analysis Plan (SAP). This protocol provides the key information, namely the justification for the sample size and the details on the primary analysis. The details regarding secondary endpoints, subgroup analyses, missing data and analysis sets are provided in the SAP. **Sample Size Determination**

In the RELAX trial, the mean \pm SD change in peak VO₂ with placebo in subjects with HFpEF treated for 6 months was 0 ± 2.0 ml/kg/min,³⁶ and in a previous trial of ET in HFpEF, the increase in peak VO in the ET arm was $+2.3\pm 2.2$ ml/kg/min.²² An increase of 75% (additional 1.5 ml/kg/min) in this change would be considered clinically relevant. Thus, we estimate that a sample size of N=34 participants per group will be required to provide 80% statistical power (two-tailed, alpha=0.05) to detect the difference of 1.5 ml/kg/min between subjects randomized to NO₂⁻ with ET versus placebo with ET. To account for attrition, we will increase our number of randomized subjects to 40/group (enroll 80 subjects total to accrue 68 total or 34 in each group).

Stage 1 was discontinued early because of loss of inhaled nitrite availability, therefore we will accrue a total of 68 patients with complete data combining the patients with complete data receiving inhaled placebo in Stage I (n=17) with another 51 patients in Stage II (17 receiving placebo and 34 receiving nitrite) to ensure that the study is adequately powered to test the study hypotheses.

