7.3 Primary Outcome Analysis

Primary Statistical Hypotheses:

H0: Change from baseline to 12 weeks in Peak VO₂ in participants randomized to NO₂⁻ will be equal to the change in Peak VO₂ in participants randomized to placebo.

Ha: The change from baseline to 12 weeks in Peak VO₂ will be different between the two randomized groups

Analysis Summary:

The primary statistical hypothesis will be tested using a regression framework. The dependent variable will be the change (baseline to 12 week) in Peak VO₂. An indicator variable will be used to indicate the randomized treatment assignment (NO₂⁻ vs. placebo as the referent). This analysis is equivalent to a two-sample t-test. While the study design is randomized, the number of participants is relatively small, so imbalance between putative confounding variables may be observed. To address this, we will conduct an a priori sensitivity analysis that will adjust for baseline Peak VO₂, BMI, Sex, and Age group strata through an extension of the regression model used for the primary analysis. The type III estimate of the treatment effect will be compared to the unadjusted estimate to assess the robustness of the randomization process.

Statistical testing for the primary analysis will be two-sided at the alpha=0.05 level of significance.

8 Safety and Adverse Events

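### The planned correlation of changes in activity, QOL and symptoms with change in RH-PAT states no term for treatment arm; pooled across arms, it would mix the two treatment effects into the association

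*Combined protocol and SAP*

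**What the plan says.** The analysis has one sentence, in the endothelial function paragraph of the study assessments (protocol section 6.5.3): "Changes in activity level, QOL and symptoms will then be correlated with changes in microvascular endothelial function (RH-PAT"). The documents do not name the coefficient, the significance level, the analysis set or any covariate.

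Four other places bear on it:

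- Section 2, Aim 2, lists among its secondary hypotheses for nitrite plus training "enhanced endothelial function and better QOL compared to ET with placebo". The same aim expects greater daily activity and fewer symptoms.
- Section 1.3 (preliminary studies for Aim 2) gives the reasoning: nitrite may help through central haemodynamics "as well as by improving microvascular endothelial function, and in so doing, improve daily activity levels".
- Section 3.3 makes "endothelial function assessed by tonometry" a secondary endpoint. It does not list the correlation.
- Section 7.1 says: "The details regarding secondary endpoints, subgroup analyses, missing data and analysis sets are provided in the SAP". The combined document as supplied contains no separate SAP text.

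For contrast, section 7.3 does specify an arm term for the peak VO2 model: "An indicator variable will be used to indicate the randomized treatment assignment".

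**The concern.** When two change scores are correlated over all patients, the coefficient has two sources: the association among patients on the same treatment, and the distance between the arm means on both measures. The second is already reported by the between-arm comparisons. It says nothing about whether patients whose endothelial function improved more also gained more activity or better QOL.

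The trial's hypotheses are the conditions under which the second source is present, since Aim 2 expects nitrite to move both sides. Section 1.3 proposes endothelial function as a pathway to activity, so a positive coefficient would naturally be read as support for that pathway. If the arms were pooled without adjustment, it could be only a restatement of two arm effects. What is at stake is the interpretation of a secondary, mechanistic analysis, not the primary result.

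**Working it through.** **The plan's own figure.** Section 7 gives the sizing as follows: "sample size of N=34 participants per group will be required to provide 80% statistical power (two-tailed, alpha=0.05"). The target is a treatment difference of 1.5 ml/kg/min in peak VO2 change. Section 7 cites SDs of change of 2.0 and 2.2 ml/kg/min from two earlier trials and does not say which was used. By the normal approximation:

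n per group = 2 × (1.960 + 0.842)² × SD² / 1.5²

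- SD 2.2: 2 × 7.849 × 4.84 / 2.25 = 33.8, so 34. This reproduces the stated figure (power 80.3%; the t-test formula gives 35, with 79.1% power at 34).
- SD 2.0: 2 × 7.849 × 4.00 / 2.25 = 27.9, so 28.

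The standardised design effect is therefore 1.5 / 2.2 = 0.68 SD. It belongs to peak VO2, which is not one of the variables in this correlation. It serves below only as one reference point.

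**Inputs for the check.**

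- Group sizes: 34 nitrite and 34 placebo with complete data, the placebo group being 17 from Stage I and 17 from Stage II (section 7). Stage II alone gives 34 and 17. The documents do not say which set the correlation uses.
- Significance level: two-sided 5%, taken from the primary analysis. None is stated for the correlation.
- Shifts between arms, in within-arm SD units: assumed, from 0.3 to 1.5 and equal on both measures. The documents give no effect size for RH-PAT, activity, KCCQ or Borg scores.
- Within-arm correlation: set to zero, so that any pooled correlation comes from the arm shifts alone.

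**Induced correlation.** With p the proportion on nitrite, q = p(1 − p), and d1, d2 the two shifts:

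r = q·d1·d2 / √[(1 + q·d1²)(1 + q·d2²)]

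For 34 v 34, q = 0.25:

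- 0.68 SD on both: 0.25 × 0.465 = 0.116; r = 0.116 / 1.116 = 0.10.
- 1.0 SD on both: r = 0.25 / 1.25 = 0.20.

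For 34 v 17, q = (2/3)(1/3) = 0.222:

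- 0.68 SD on both: 0.222 × 0.465 = 0.103; r = 0.103 / 1.103 = 0.09.
- 1.0 SD on both: r = 0.222 / 1.222 = 0.18.

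The observed |r| needed for significance is 0.239 with 68 patients and 0.276 with 51.

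**Rejection rates.** From 40,000 simulated trials per setting, bivariate normal with zero within-arm correlation:

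| Shift on both measures | r, 34 v 34 | Pooled test, 34 v 34 | Arm-adjusted test, 34 v 34 | Pooled test, 34 v 17 |
|---|---|---|---|---|
| 0.3 SD | 0.02 | 5.2% | 4.9% | 5.3% |
| 0.5 SD | 0.06 | 7.8% | 5.1% | 6.6% |
| 0.68 SD | 0.10 | 13.9% | 5.0% | 10.1% |
| 0.8 SD | 0.14 | 20.4% | 4.9% | 13.9% |
| 1.0 SD | 0.20 | 38.4% | 4.9% | 25.0% |
| 1.5 SD | 0.36 | 89.5% | 5.1% | 70.8% |

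With a 0.68 SD shift on one measure and none on the other, r is 0 and the pooled test rejects in 5.1% of trials in either layout. The arm-adjusted test stays between 4.8% and 5.1% in every setting, including 34 v 17.

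**The case against.** The strongest reply is that the missing adjustment is inferred from silence. The sentence stands in a description of assessments, not in the statistical section. Section 7.1 limits the protocol to the sample size and the primary analysis and sends secondary endpoints to the SAP, so the lack of an arm term here is not proof that none is intended. This stands: a reader might infer that the plan commits the trial to an unadjusted correlation, and the documents do not say so. But the deferral does not settle the matter either. Section 3.3 does not list the correlation as an endpoint, and nothing supplied shows that the SAP covers it.

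A reader might also infer that the trial will present this correlation as its test of mechanism, or that a pooled analysis would reliably produce a spurious link. Neither is supported. Section 6.5.3 states no hypothesis, test or conclusion for it, and the pathway idea is background in section 1.3. On size, a 0.68 SD shift on both measures leaves about 86% of trials non-significant (100 − 13.9), and that shift is borrowed from peak VO2.

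Finally, the excess rejections are false positives only if the target is the within-arm association. If the question is merely whether the two changes occur together across all patients, a non-zero pooled value describes that correctly. This is fair, but the within-arm association is the one that bears on the pathway in section 1.3. Nor would adjustment settle mechanism: common causes within an arm, such as training adherence, remain.

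**Conclusion.** The point holds as a gap in specification with a clearly better method available. The supplied text plans a correlation and states no arm term, while the trial's own hypotheses are that treatment moves both sides of it. A simple correlation pooled across arms would then carry the arm effects.

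The size is conditional. It rests on assumed equal shifts, zero within-arm correlation, normal data, a nominal 5% test and, for the main figures, a 34 v 34 set. The artefact is negligible at 0.3 SD, modest at 0.5 to 0.68 SD, serious only near 1 SD or more on both measures, and absent if only one measure shifts. It is somewhat smaller in Stage II alone. This is a minor point about a secondary analysis.

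**What to change.** In the endothelial function paragraph of section 6.5.3, or in the SAP with a cross-reference there:

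- Estimate each association by partial correlation given treatment arm, or by regressing the outcome change on RH-PAT change with arm as a covariate.
- Add stage as a covariate if Stage I placebo patients are included. They all sit on the placebo side and, unlike Stage II patients, used a nebuliser. Because placebo patients come from both stages, a stage term can be estimated alongside arm.
- Report the within-arm associations.
- Label the analysis exploratory, and note that an arm-adjusted association does not prove mediation.

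The cost is a line or two of text and one degree of freedom for arm, plus one for stage where it is used. No new data are needed. The change is best made before unblinding. If the SAP already specifies this, a cross-reference is enough.
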